NON-INTERVENTIONAL (NI) STUDY PROTOCOL

Study information

Title Protocol number Protocol version identifier Date EU Post Authorization Study (PAS) registor number	Real-World Observational Study of Outcomes for Acute Myeloid Leukemia (AML) Patients Treated With Glasdegib or Venetoclax in US Community Oncology PracticesB1371039Final11 May 2020Not yet registered		
Active substance	glasdegib		
Medicinal product	DAURISMO ™		
Research question and objectives	 Primary Document and understand the demographic, clinical, and disease-related characteristics of AML patients who initiated treatment with a glasdegib (GLAS)-based regimen. Assess treatment patterns of AML patients who initiated treatment with GLAS-based regimen (regimen, cycles, dose details, duration of therapy by line of therapy up to 2 lines). Estimate the clinical outcomes of AML patients who initiated treatment with GLAS-based regimen.		

PFIZER CONFIDENTIAL

CT24-WI-GL02-RF02 1.0 Non-Interventional Study Protocol Template For Secondary Data Collection Study 15-Aug-2018 Page 1 of 35

	 Document and understand the patient demographic, clinical, and disease-related characteristics of AML patients who initiated treatment with a venetoclax (VEN)-based regimen.
	5) Assess treatment patterns of AML patients who initiated treatment with a VEN-based regimen (regimen, cycles, dose details, duration of therapy by line of therapy up to 2 lines).
	 6) Estimate the clinical outcomes of AML patients who initiated treatment with a VEN based regimen. a. TI, disease response, EFS/RFS, and of for AML patients treated with a VEN based regimen. b. Treatment related toxicities and adverse events (AEs) related to AMI patients who initiated treatment with VEN-based regimens (type of Grade or 4 AEs, date of AE, emergency department visits and hospitalization related to management of AEs).
Author	[name], MPH
	Lead Scientist, Real-World Evidence & Insights
	Cardinal Health Specialty Solutions
	Email: [contact]
	[contact]

This document contains confidential information belonging to Pfizer. Except as otherwise agreed to in writing, by accepting or reviewing this document, you agree to hold this information in confidence and not copy or disclose it to others (except where required by applicable law) or use it for unauthorized purposes. In the event of any actual or suspected breach of this obligation, Pfizer must be promptly notified.

2. LIST OF ABBREVIATIONS

Abbreviation	Definition
AE	adverse event
AEM	adverse event monitoring
ALP	alkaline phosphatase
ALT	alanine transaminase
AST	aspartate transaminase
AML	acute myeloid leukemia
AZA	azacitidine
CHSS	Cardinal Health Specialty Solutions
CI	confidence interval
CR	complete response
CRF	case report form
CRh	complete response with partial hematologic recovery
CRi	complete response with incomplete hematologic recovery
СҮРЗА	cytochrome P450 3A
DEC	decitabine
DOR	duration of response
eCRF	electronic case report form
ED	emergency department
EFS	event-free survival
EMR	electronic medical record
FDA	Food and Drug Administration
GCSF	granulocyte colony-stimulating factor receptor

PFIZER CONFIDENTIAL

CT24-WI-GL02-RF02 1.0 Non-Interventional Study Protocol Template For Secondary Data Collection Study 15-Aug-2018 Page 5 of 35

Abbreviation	Definition
GGT	gamma-glutamyltransferase
GLAS	glasdegib
HIPAA	Health Insurance Portability and Accountability Act
НМА	hypomethylating agent
HR	hazard ratio
IEC	Independent Ethics Committee
IRB	Institutional Review Board
ISPE	International Society for Pharmacoepidemiology
КМ	Kaplan-Meier
LDAC	low-dose cytarabine
MDS	myelodysplastic syndrome
MLFS	morphologic leukemia-free state
NIS	non-interventional study
OPEN	Oncology Provider Extended Network
OS	overall survival
PD	progressive disease
PHI	Protected Health Information
PR	partial response
RBC	red blood cell
RFS	relapse-free survival
SAE	serious adverse events
SAP	Statistical Analysis Plan
SD	stable disease

CT24-WI-GL02-RF02 1.0 Non-Interventional Study Protocol Template For Secondary Data Collection Study 15-Aug-2018 Page 6 of 35

Abbreviation	Definition
SD	standard deviation
STROBE	Strengthening the Reporting of Observational Studies in Epidemiology
TD	transfusion dependence/dependent
TI	transfusion independence/independent
US	United States
VEN	venetoclax
WBC	white blood cell

4. ABSTRACT

Title

Real-World Observational Study of Outcomes for Acute Myeloid Leukemia (AML) Patients Treated With Glasdegib or Venetoclax in US Community Oncology Practices

Final, 01 May 2020

Main Author: [name], MPH, Cardinal Health Specialty Solutions

Rationale and background

Glasdegib (GLAS) and venetoclax (VEN) were approved in November 2018 for the treatment of AML in patients who are 75 years old or older or who have comorbidities that preclude intensive induction chemotherapy. Limited real-world observational studies of treatment patterns and outcomes for patients treated with either therapy have been conducted.

Research question and objectives

Primary 199

- 1) Document and understand the patient demographic, clinical, and disease-related characteristics of AML patients who initiated treatment with a GLAS-based regimen.
- 2) Assess treatment patterns of AML patients who initiated treatment with GLAS-based regimen (regimen, cycles, dose details, duration of therapy by line of therapy up to 2 lines).
- 3) Estimate the clinical outcomes of AML patients who initiated treatment with GLASbased regimen.
 - a. Transfusion independence (TI), disease response, event-free/relapse-free survival (EFS/RFS), and overall survival (OS) for AML patients treated with GLAS-based regimen.

Secondary

- 4) Document and understand the patient demographic, clinical, and disease-related characteristics of AML patients who initiated treatment with a VEN-based regimen.
- 5) Assess treatment patterns of AML patients who initiated treatment with a VEN-based regimen (regimen, cycles, dose details, duration of therapy by line of therapy up to 2 lines).
- 6) Estimate the clinical outcomes of AML patients who initiated treatment with a VENbased regimen.
 - a. TI, disease response, EFS/RFS, and OS for AML patients treated with a VENbased regimen.
 - b. Treatment related toxicities and adverse events (AEs) related to AML patients who initiated treatment with VEN-based regimens (type of Grade 3 or 4 AEs,

PFIZER CONFIDENTIAL

CT24-WI-GL02-RF02 1.0 Non-Interventional Study Protocol Template For Secondary Data Collection Study 15-Aug-2018 Page 9 of 35

date of AE, emergency department [ED] visits, and hospitalizations related to management of AEs).

Study design

Retrospective medical chart review of US patients with AML treated with either a GLAS- or VEN-based regimen between 01 December 2018 and 31 December 2019. Up to 150 GLASor VEN-treated patients will be included. The study will be conducted in 5 sequential phases: Phase 1 (study concept feasibility) assesses the number of providers who have prescribed GLAS to an AML patient in Cardinal Health research network and the providers' willingness to participate in the research. Phase 2 tests the electronic data capture tool for clinical/operational functionality. Phase 3 (study conduct feasibility) will collect data on up to 15 patients treated with GLAS among providers who have completed all required AE reporting and data abstraction training and report having treated at least 1 eligible patient with GLAS specifically. Pfizer will evaluate based on the characteristics, treatment patterns, and outcomes of the 15 patients from Phase 3 to determine whether to proceed with further data collection. Phase 4 expands the GLAS cohort to include all patients treated with GLAS (Phase 4a), or a random selection, potentially including those who received GLAS as secondline or greater (pending the results of Phase 3), by those providers who participated in Phase 3. After data collection of all GLAS-treated patients is completed, and at the discretion of Pfizer, data collection for patients treated with VEN will occur (Phase 4b). Additional waves (a maximum of 3) of long-term follow-up (or if appropriate, the recruitment of new patients) successively in 4-month increments may occur after completion of all data collection for patients alive at each interval (Phase 5a-c, as applicable).

Population

- 1. Patients newly diagnosed with AML.
- 2. Initiated first-line or later therapy (ie, index therapy) for newly diagnosed AML with GLAS-based regimen (allowable combinations include GLAS plus low-dose cytarabine, GLAS plus azacytidine, or GLAS plus decitabine) or initiated first-line therapy with VEN-based regimen (allowable combinations including VEN plus low-dose cytarabine, VEN plus azacytidine, or VEN plus decitabine) in the following time periods*:
 - a. Initiated first-line or later therapy for AML with any GLAS-based regimen between 01 December 2018 and 31 December 2019.^{\dagger}
 - b. Initiated first-line therapy for AML with any VEN-based regimen between 01 December 2018 and 31 December 2019.

* These patients could have received systemic therapy for myelodysplastic syndrome (MDS, a precursor disease to AML, prior to diagnosis of AML).

† Patients who received GLAS as second-line or greater may be selected in Phase 4a pending the results of Phase 3.

3. ≥ 18 years of age at index therapy initiation.

PFIZER CONFIDENTIAL

CT24-WI-GL02-RF02 1.0 Non-Interventional Study Protocol Template For Secondary Data Collection Study 15-Aug-2018 Page 10 of 35

- 4. ≥ 6 months of follow-up from initiation of index therapy unless the patient died, with known date of death.
- 5. Known cytogenetic risk profile at the time of index therapy initiation as defined below in Section 8.4.
- 6. ≥ 1 bone marrow biopsy completed following index therapy initiation.

Patients meeting any of the following criteria will not be included in the study:

- 1. Patients who received treatment for AML as part of a clinical trial.
- 2. Patients with diagnosis of any other malignancy (except for non-melanoma skin cancer) at the time of treatment of AML.
 - a. Patients with diagnosis of AML and non-melanoma skin cancer at the time of treatment of AML will not be excluded.
- 3. A patient with a record of 1 or more of the following confounding diagnoses at any time during data availability: acute lymphoblastic leukemia; acute promyelocytic leukemia, aggressive systemic mastocytosis; hypereosinophilic syndrome and/or chronic eosinophilic leukemia; dermatofibrosarcoma protuberans; or gastrointestinal stromal tumors.

Variables

Patient demographics, clinical characteristics, and treatment patterns will be collected. In addition, patients response to GLAS or VEN therapy, dates of disease progression, toxicities occurring during treatment (VEN cohort only), and date of death/last follow-up will be abstracted.

Data sources

The patient's treating physician will abstract data from the patient's electronic health record into the data capture forms. All study data are secondary. Providers will be trained on data collection to ensure accuracy and reliability. No protected health information, except for dates of diagnosis, treatment, and outcomes, will be collected. The patients electronic medical record will not be shared directly with Cardinal Health or Pfizer.

Study size

The total proposed sample size across the 2 treatment arms is 150 patients.

Data analysis

Each cohort will be described independently; no comparisons of patient characteristics or outcomes between GLAS- and VEN-treated patients will be conducted. The primary clinical outcomes of interest include TI, duration of therapy, disease response, duration of response, EFS, RFS, and OS. Time to event outcomes will be analyzed using the Kaplan-Meier

PFIZER CONFIDENTIAL

CT24-WI-GL02-RF02 1.0 Non-Interventional Study Protocol Template For Secondary Data Collection Study 15-Aug-2018 Page 11 of 35

method. Comparisons of time to event outcomes will be made using a Cox proportional hazards model or other parametric techniques as appropriate. Experience of toxicities will only be described for the VEN-treated cohort. Details of the data analysis will be provided in the statistical analysis plan.

Milestones

- Completion of feasibility assessment: Q2 2020
- Registration in the EU PAS register: Q2 2020
- Start of data collection: Q2 2020
- End of data collection: Q3 2020
- Final study report: Q4 2020

5. AMENDMENTS AND UPDATES

None

6. MILESTONES

Milestone	Planned date
Project kickoff	27 August 2019
Study protocol development	Q2 2020
Study protocol finalization/approval	Q2 2020
Case report form (CRF) development	Q2 2020
CRF finalization/approval	Q2 2020
Registration in the EU PAS register	Q2 2020
Institutional review board (IRB) preparation/submission/approval	Q2 2020
Statistical Analysis Plan (SAP) & table shells	Q2 2020
SAP & table shells finalization/approval	Q2 2020
Electronic CRF (eCRF) programming & testing	Q2 2020
Phase 2: eCRF pre-test (n=4)	Q2 2020
Phase 3: study conduct feasibility (n=15)	Q2 2020
Phase 3: data analysis	Q3 2020
Phase 4a/b: GLAS/VEN data collection expansion (n=150)	Q3 2020
Phase 4: data analysis	Q4 2020
Final study report (assume after Phase 4)	Q4 2020
Phase 5: long-term follow-up data collection (optional)	Q1 2021
Updated analyses	Q2 2021
Updated study report	Q2 2021

PFIZER CONFIDENTIAL

CT24-WI-GL02-RF02 1.0 Non-Interventional Study Protocol Template For Secondary Data Collection Study 15-Aug-2018 Page 14 of 35

7. RATIONALE AND BACKGROUND

Acute Myeloid Leukemia (AML) is the most common form of fast-growing blood and bone marrow cell cancer. In the United States (US) in 2019, it is estimated there will be 21,450 new cases and 10,920 deaths from AML.¹ The average age at diagnosis is 68 years old, and the 5-year survival rate is 26.9%.² About 60%-70% of adults with AML can attain a complete remission following induction therapy with cytotoxic chemotherapies to reduce leukemic cells in the blood and bone marrow. Slightly more than 25% (45% of those who attain complete remission) are expected to survive 3 or more years and may be cured.² Remission rates are related to age, with the expected remission rate of more than 65% in those younger than 60 years old. Duration of remission is shorter in older patients, and increased morbidity and mortality during induction treatment are related to older age.²

Treatment of AML in elderly patients is particularly challenging due to higher comorbidity loads and the general toxicity of intensive treatments. Historically, the number of treatments available for newly diagnosed patients with AML for whom intensive chemotherapy is not an option has been limited (eg, low-dose cytarabine [LDAC], azacitidine [AZA], decitabine [DEC]). New treatment regimens have become available within the last 2 years including: glasdegib (GLAS) plus LDAC; venetoclax (VEN) plus hypomethylating agents (HMAs), AZA, DEC, or LDAC; and gemtuzumab ozogamicin. More novel regimens are currently in advanced clinical development. Given the potential for a dramatic change in how patients are treated, it is critical to understand the evolution of non-intensive chemotherapy AML treatment over the next several years.

Limited real-world observational studies of treatment patterns, outcomes, and safety for patients treated with either therapy have been conducted. Given the potential for a dramatic change in how patients are treated, it is critical that the scientific and medical communities continue to work to document the evolution of AML treatment over the coming years. The present study is focused on real-world outcomes in adult patients with AML who in the frontline received non-intensive therapy defined as GLAS-based (including GLAS+LDAC, GLAS+AZA, or GLAS+DEC) or VEN-based therapy (including VEN+LDAC, VEN+AZA, or VEN+DEC) in combination with other agents. Although the present study is focused on the receipt of this therapy during first-line therapy, it is expected that most of the identified patients will also go on to receive subsequent treatment. The aim of this study is to describe treatment patterns and effectiveness outcomes in a sample of oncology patients treated for AML with non-intensive first-line treatments.

This non-interventional study is designated as a Post-Authorization Safety Study (PASS) and is conducted voluntarily by Pfizer.

8. RESEARCH QUESTION AND OBJECTIVES

As GLAS- and VEN-based therapies for AML have only recently been approved in the US, patient profile and clinical outcomes of AML patients receiving GLAS- or VEN-based therapies have limited documentation. This study seeks to analyze real-word patient characteristics and clinical outcomes in patients with AML who receive frontline therapy with GLAS-based regimen or VEN-based regimen. The following objectives are prespecified for this retrospective cohort study of patients with AML using a chart review methodology.

Primary 199

1) Document and understand the patient demographic, clinical, and disease-related characteristics of AML patients who initiated treatment with a GLAS-based regimen.

PFIZER CONFIDENTIAL

CT24-WI-GL02-RF02 1.0 Non-Interventional Study Protocol Template For Secondary Data Collection Study 15-Aug-2018 Page 16 of 35

- 2) Assess treatment patterns of AML patients who initiated treatment with GLAS-based regimen (regimen, cycles, dose details, duration of therapy by line of therapy up to 2 lines).
- 3) Estimate the clinical outcomes of AML patients who initiated treatment with GLASbased regimen.
 - a. Transfusion independence (TI), disease response, event-free/relapse-free survival (EFS/RFS), and OS for AML patients treated with GLAS-based regimen.

Secondary

- 4) Document and understand the patient demographic, clinical, and disease-related characteristics of AML patients who initiated treatment with a VEN-based regimen.
- 5) Assess treatment patterns of AML patients who initiated treatment with a VEN-based regimen (regimen, cycles, dose details, duration of therapy by line of therapy up to 2 lines).
- 6) Estimate the clinical outcomes of AML patients who initiated treatment with a VENbased regimen.
 - a. TI, disease response, EFS/RFS, and OS for AML patients treated with a VENbased regimen.
 - b. Treatment related toxicities and adverse events (AEs) related to AML patients who initiated treatment with VEN-based regimens (type of Grade 3 or 4 AEs, date of AE, emergency department [ED] visits, and hospitalizations related to management of AEs).

9. RESEARCH METHODS

9.1. Study design

This study will be conducted through a multi-site medical chart review of AML patients treated at oncology clinics in the US. Providers in the Cardinal Health Oncology Provider Extended Network (OPEN) will be recruited to participate in the patient identification and data abstraction. All study data are secondary data and will have been collected retrospectively from existing clinical data originally collected as part of routine care.

Patient eligibility will be confirmed by the treating physician. Providers will abstract the patient level data necessary to achieve the research objectives into an electronic case report form (eCRF). No protected health information, except for dates of diagnosis, treatment, and outcomes, will be collected. The patients electronic medical record (EMR) will not be shared directly with Cardinal Health or Pfizer.

Two different types of AML patient cohorts will be identified as follows:

• GLAS-based: initiated first-line or later therapy (eg, index therapy) with GLAS+AZA, GLAS+DEC, GLAS+LDAC between 01 December 2018 and 31

PFIZER CONFIDENTIAL

CT24-WI-GL02-RF02 1.0 Non-Interventional Study Protocol Template For Secondary Data Collection Study 15-Aug-2018 Page 17 of 35 December 2019 (allowable combinations include GLAS plus low-dose cytarabine, GLAS plus azacytidine, or GLAS plus decitabine)

• VEN-based: initiated first-line (index) therapy with VEN+AZA, VEN+DEC, VEN+LDAC between 01 December 2018 and 31 December 2019 (allowable combinations including VEN plus low-dose cytarabine, VEN plus azacytidine, or VEN plus decitabine)

The study will be conducted in 5 sequential phases. The total proposed sample size across the 2 treatment arms is 150 patients. Figure 1 illustrates the study period.

Phase 1: Study Concept Feasibility

Cardinal Health Specialty Solutions (CHSS) research operations team, the investigator, will conduct outreach to OPEN inquiring as to the number of physicians who have prescribed GLAS per the study selection criteria. Providers will also be queried regarding their acceptance of the rules and conditions associated with participation in the research study.

Phase 2: eCRF Testing

A total of 4 community oncologists will review the eCRF and abstract data for the purposes ensuring the requested clinical datapoints are available, the intent of the data point is clear, and the eCRF functions appropriately. Providers who participate in this testing phase are able to participate in further data collection. To test the eCRF providers will select 1 AZA-treated patient and complete data abstraction while Cardinal Health Specialty Solutions (CHSS) research operations team members watch data entry (via screen sharing), respond to questions from the providers, and ask questions of the providers as necessary. No data from this phase will be used in the final analytical dataset. After completion of eCRF testing, revisions to the eCRF will be made as necessary prior to the launch of study data collection.

Phase 3: Study Conduct Feasibility

CHSS will invite 15 providers who have indicated previously treating a patient with GLAS to participate in Phase 3. In Phase 3, each provider will abstract data for 1 GLAS-treated patient, randomly-selected, per the study selection criteria for a total of 15 patients. Providers will abstract data into the eCRF during a web-based, screen-sharing session with a member of the CHSS research operations team. Demographic, clinical, and disease-related characteristics of these patients, treatment patterns, and clinical outcomes will be described. After evaluating these data, Pfizer may elect to discontinue the study and not collect further data for either GLAS- or VEN-treated patients.

Phase 4a: GLAS Data Collection Expansion

Based on the results of Phase 3, Pfizer may elect to continue data collection. In addition, Pfizer may elect to expand data collection to include patients who received a GLAS-based regimen as second-line or greater should sufficient sample sizes of those patients be discovered during Phase 3 when provider enumerate all patient for whom they have prescribed a GLAS-based regimen. CHSS will allow data abstraction for the maximum number of GLAS-treated patients up to the total *a priori* sample size of 150 patients.

PFIZER CONFIDENTIAL

CT24-WI-GL02-RF02 1.0 Non-Interventional Study Protocol Template For Secondary Data Collection Study 15-Aug-2018 Page 18 of 35

Depending upon the number of GLAS-treated patients and the length of follow-up for these patients, Pfizer may elect to discontinue the study and not collect data for the VEN-treated cohort.

Phase 4b: VEN Data Collection

Should Pfizer elect to proceed with further data collection, CHSS will initiate Phase 4b, which will collect data for VEN-treated patients from those initial providers who participated in Phase 3 data collection. At the end of data collection, summary results for the VEN-treated patients will be provided.

Phase 5: Long-Term Follow-Up

As a retrospective observational study with an index period of 1 year between December 2018 and December 2019, longer follow-up of patients may be required to observed clinical outcomes of interest. As such, at the conclusion of the initial phases of data collection, additional wave(s) of follow-up may occur approximately 4 months later (a maximum of 3 additional updates, Phases 5a-c as applicable). The records of patients who were alive at the time of the initial data collection will be updated. In addition, new patients may be included during the follow-up periods; however, the total sample size is currently set at 150 regardless of when the patient was entered into the study.

Figure 1. Study Period*

*Initial data collection (Phase 3) lasts for 4 weeks. Exact start date of data collection may vary. Subsequent extended follow-ups at Pfizer discretion. Study may be stopped at any time post a data collection point.

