9.1.1. Other Aspects of Study Design

All clinicians who participate in this research will be required to complete Pfizer training related to the identification and reporting of AEs/serious adverse events (SAEs) and data abstraction training. AE/SAE training materials will be provided to the participating clinicians prior to any data collection. Once the provider has completed (electronically signed) the AE/SAE training, the providers will participate in a web-based data abstraction training. During this virtual training, CHSS research operations team members will review the AE/SAE training and answer any questions from providers. During this session, the providers will be asked to review their EMR systems to identify all patients treated with a GLAS-based regimen per the study selection criteria and generate a unique numeric identifier

for each patient. The total number of patients will be noted, including patients who received a GLAS-based regimen as second-line or greater, and the identifier maintained by CHSS research operations and the provider. CHSS will then ask the provider to randomly select one of the GLAS-treated patients. To randomly select patients, providers will sequentially number patients and provide those sequential numbers to CHSS Research Operations who will then use a random number generator to select one of the numeric patient identifiers. Providers will launch the data collection platform (web-based) and begin data abstraction for the patient. CHSS research operations will clarify any data points during this data collection process and observe the provider entering data into eCRF. After completing data abstraction, the providers will be sent electronic links to complete data abstraction for all remaining GLAS-treated patients over the course of the next 4 weeks. Providers will be given randomly selected patient numbers from the list of all GLAS-treated patients (excluding the 1 patient already submitted) and asked to complete data abstraction in the order of the randomly selected patients for the remaining patients.

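### The 15 Phase 3 glasdegib records are taken about a quarter before the rest and are not updated before the final report; the timing sections also conflict

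*Protocol*

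**What the plan says.** Section 9.1 sets up Phase 3 so that "each provider will abstract data for 1 GLAS-treated patient, randomly-selected, per the study selection criteria for a total of 15 patients". The sponsor then evaluates these data and decides whether to go on to Phase 4a, which expands the GLAS cohort. Only the Phase 2 test data are kept out of the analysis dataset (Sections 9.1 and 9.2), so the 15 Phase 3 patients remain in the cohort that serves the primary objectives.

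Section 6 dates Phase 3 collection to Q2 2020, Phase 3 analysis and Phase 4a/b collection to Q3 2020, and the report to Q4 2020: "Final study report (assume after Phase 4". The Abstract agrees: "End of data collection: Q3 2020".

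Existing records are updated only in Phase 5: "at the conclusion of the initial phases of data collection, additional wave(s) of follow-up may occur approximately 4 months later". Section 6 lists that phase as optional, in Q1 2021, and the note to Figure 1 leaves further follow-up to the sponsor's discretion.

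Section 9.1.1 describes a different sequence. Once the first chart is done, the provider receives links for all remaining GLAS charts, to be completed over the next 4 weeks in random order, "excluding the 1 patient already submitted".

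**The concern.** On the milestone dates, the final GLAS analysis combines records from two collection windows. The 15 Phase 3 records stay as they stood in Q2 2020, although the same providers are abstracting GLAS charts again in Q3. Deaths, relapses, treatment stops and late responses that reach those charts in between would not appear in the Q4 2020 report. If Phase 5 is not run, that report is the only result.

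The cohort may be small, Section 9.7.3 plans landmarks out to 12 months, and Section 9.1 itself says longer follow-up may be needed to observe the outcomes. Section 9.1 also lets the sponsor drop the venetoclax cohort depending on the length of GLAS follow-up, so records that have not been updated would feed that decision too.

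**Working it through.** The protocol gives no figure for this point, so the check sets its dates side by side and then sizes the loss under stated assumptions.

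**1. Is any update planned before the report?** The order in Section 6 is Phase 3 (Q2), Phase 3 analysis and Phase 4 (Q3), final report (Q4), optional Phase 5 (Q1 2021). Section 9.1 provides for updates in Phase 5 only. The Section 9.1.1 sequence does not return to the first chart either. No update is planned on either account.

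**2. How long is the gap?**
- Section 9.1.1: about 4 weeks at most.
- Section 6, mid-Q2 to mid-Q3 (15 May to 15 August 2020): 92 days, about 3 months.
- Upper limit, from the protocol date (11 May) to the end of Q3 (30 September): 142 days, about 4.7 months.

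The 4-week sequence cannot be squared with a sponsor decision on Phase 3 data before Phase 4a, nor with the Q2/Q3 split.

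**3. What share of the GLAS cohort are the 15?** The final number is not fixed.
- Feasibility count (Section 9.5): 15/39 = 38.5%.
- Feasibility rate applied to 15 providers: 39/11 × 15 ≈ 53, and 15/53 = 28.3%.
- Ceiling in Section 9.1: 15/150 = 10%.

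The share exceeds one third only up to 44 patients (15/44 = 34.1%; 15/45 = 33.3%). The 39 is a prescribing count, so losses to the eligibility criteria in Section 9.2.1 could lower the number and raise the share.

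**4. How many lose overall survival (OS) follow-up?** Assumptions: start dates uniform over the 395 days from 1 December 2018 to 31 December 2019, exponential survival, and data dates of 15 June and 31 August 2020 (562 and 639 days after 1 December 2018). The median of 8.3 months appears in Section 7 in an incomplete sentence and serves here only as an assumption. The 6-month and biopsy criteria are ignored.

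Proportion alive at day c = [exp(−λ(c−395)) − exp(−λc)] / (395λ), with λ = ln 2/(8.3 × 30.4375) = 0.002744 per day.
- Day 562: (0.632 − 0.214)/1.084 = 0.386, and 15 × 0.386 = 5.8 alive.
- Day 639: (0.512 − 0.173)/1.084 = 0.313, and 15 × 0.313 = 4.7 alive.
- Deaths not recorded: 5.8 − 4.7 = 1.1.

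With medians of 6 and 12 months, 4.1 and 7.7 of the 15 are alive on 15 June, and about 1.0 death goes unrecorded in each case. Across these medians, a 4-week gap from 15 June leaves about 0.4 deaths unrecorded, and the 142-day limit about 2.

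**5. Potential 12-month follow-up.** Patients who started by 15 June 2019: 196/395 = 50%. Patients who started by 31 August 2019: 273/395 = 69%.

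**6. Effect on precision.** In simulated cohorts of 39 under the step 4 assumptions (8.3-month median), with and without updating the 15, expected deaths rise from about 25.8 to 26.8. The mean Greenwood standard error of 12-month OS falls from 0.082 to 0.080. The 95% half-width moves from 1.96 × 0.082 = 16.1 to 1.96 × 0.080 = 15.7 percentage points.

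**The case against.** The strongest reply is that the effect is very small, and it is. One extra death and 0.4 percentage points of half-width are minor beside a 13-month spread of start dates. Kaplan-Meier estimation with censoring at each patient's last visit already handles unequal follow-up, and the Phase 3 patient is chosen at random within each provider.

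A second reply is that Section 9.1.1 reduces the gap to about 4 weeks. On that text it does, but the text conflicts with Sections 6 and 9.1, and the first chart still goes without an update. Its exclusion of the submitted patient only removes that patient from the random draw; it does not forbid an update.

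A third reply is that the protocol already provides for longer follow-up, with up to three further waves and an updated report in Q2 2021. That is true, but all of it is optional and comes after the final report.

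A reader might infer that over a third of the primary cohort has less follow-up. The documents do not support that. The share depends on a cohort size that is not fixed, and patients already dead at Phase 3 lose no OS follow-up. At n=39 the patients affected for OS are about 5.8/39 = 15%. A reader might also take the reference to a data cut-off in Table 9.3.1 as a promise of one common date. The table does not say so, and Section 9.3 leaves detailed definitions to the statistical analysis plan and case report form.

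**Conclusion.** The point holds in limited form. By the milestone table, the 15 Phase 3 patients are abstracted about a quarter before the remaining GLAS patients, and nothing updates their records before the Q4 2020 report. Sections 6, 9.1 and 9.1.1 disagree on when the remaining charts are abstracted.

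The 15 make up 10% to 38% of the cohort for final sizes from 150 down to 39. Of them, about 4 to 8 would be alive at Phase 3 and lose OS follow-up. The expected cost is about one unrecorded death and a slightly larger standard error. These sizes rest on the assumed medians, uniform starts and data dates; the effects on event-free and relapse-free survival, duration of response and response were not quantified.

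A reader might infer bias in the survival estimates. Given random selection within provider and censoring at last visit, the documents show lost information and no demonstrated bias. This is a low-priority improvement, worth making because it is cheap.

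**What to change.** Add to Phase 4a in Section 9.1 that each Phase 3 provider updates the follow-up fields (end of index therapy, best response, relapse, transfusions, vital status and last visit) of the Phase 3 patient, unless that patient is already recorded as dead. Do this in the same 4-week window as the remaining GLAS charts. All GLAS patients are then followed to the same Phase 4 collection window, though not to a single calendar date.

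Reconcile Sections 6, 9.1 and 9.1.1, so that the protocol states once whether the remaining GLAS charts follow the first within 4 weeks or wait for the sponsor's decision after Phase 3.

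The cost is roughly 4 to 8 short chart updates by providers who are already abstracting, with the related payment. No new patients or sites are needed.
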